5.1.3.2 Response Follow-up Period (Parts 1A, 1B, 1C, 2A, 2B, and 2C)

Participants, with SD, PR, or CR, at the time of the EOT visit or at the time of study drug discontinuation, will continue to have radiologic and clinical tumor assessments every 12 weeks for the first year after discontinuation of study drug/EOT visit. Subsequently, they will continue to receive tumor assessment scans as per standard of care guidelines, or at a minimum of every 6 months up to 2 years following the last dose of study drug, or until disease progression/withdrawal of study consent. Radiological assessments for participants who have ongoing clinical benefit may continue to be collected after participants complete the survival follow-up period of the study. Participants who have disease progression following an initial course of study therapy will not be evaluated for response beyond the EOT visit, and will be allowed to receive other tumor directed therapy as required.

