Vital Signs and Oxygen Saturation	X	X	X	X	X	X	X	X		
ECGs	X						X		X	ECGs should be recorded after the participant has been supine for at least 5 minutes, and prior to blood draws. Single safety ECGs to be done on Day 1 of all treatment cycles.
Adverse Event Assessments	Continuously during the study								All SAEs must be collected from the date of the participant's written consent until 100 days following the last dose of study drug. All AEs (including SAEs and non-serious AEs), including those associated with SARS-CoV-2 infection, must be collected continuously during the treatment period.	
Review of Concomitant Medications	X	X	X	X	X	X	X	X	X	

Table 2-4: On Treatment- Schedule of Activities -Triplet Cohort (Part 1C) and Triplet NSCLC Expansion (Part 2C)

Procedure	Cycle 1 Visit Window = -3 Days for C1D1, ± 3 Days for All Others						Each Subsequent Cycle		EOT	Notes 1 Cycle = 6 weeks
	D1	D8	D15	D22	D29	D36	D1 (± 3 Days)	D22 (± 3 Days)		
Pregnancy Test (WOCBP only)	X			X			X	X	X	For WOCBP; serum/urine pregnancy test to be performed (urine pregnancy test: minimum sensitivity 25 IU/L or equivalent units of hCG), see Section 9.2.5 .
ECOG Performance Status	X						X			Confirm status prior to randomization and on C1D1
Laboratory Assessments										
Chemistry and hematology tests	X			X			X	X		Within 72 hrs prior to dosing. See 9.4.4 and Table 9.4.4-1 .

Table 2-4: On Treatment- Schedule of Activities -Triplet Cohort (Part 1C) and Triplet NSCLC Expansion (Part 2C)

Procedure	Cycle 1 Visit Window = -3 Days for C1D1, ± 3 Days for All Others						Each Subsequent Cycle		EOT	Notes 1 Cycle = 6 weeks		
	D1	D8	D15	D22	D29	D36	D1 (± 3 Days)	D22 (± 3 Days)				
Efficacy Assessments												
Body Imaging	Contrast enhanced CT of the chest, CT/MRI of the abdomen, pelvis, and all other known and/or suspected sites of disease should occur every 6 weeks starting from date of first dose (± 7 days) for the first 12 months (week 48), then every 12 weeks (± 7 days) until the end of year 2, then every 12 weeks (± 14 days) thereafter until disease progression or treatment discontinuation, whichever occurs later. See Section 9.1 and Section 5.1.4 for further details.											

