^a Only participants with SD, PR, or CR at EOT visit. After first year of response follow-up, participants will continue to receive tumor assessment scans as per standard-of-care guidelines, or at a minimum of every 6 months for a total of 2 years response follow-up after the last dose of study drug.

^b Follow-up visits at Days 30, 60 (± 7days), and 100 (± 10days) should occur relative to the last dose of study drug or date of discontinuation.

^c For details of laboratory tests, see [Section 9.4.4](#) and [Table 9.4.4-1](#).

Table 2-6: Retreatment Day 0 Procedural Outline (Parts 1A, 1B, 2A, 2B only)

Procedure	Day 0 ^{a,b}	Notes
Eligibility Assessments	X	Participants must meet eligibility criteria and discussion with BMS Medical Monitor should occur.
Safety Assessments		
Physical Examination	X	If the screening physical examination is performed within 72 hours of dosing on re-treatment Cycle 1/Day 1, then a single examination may count as both the screening and predose evaluations.
ECOG Performance Status	X	
Physical Measurements	X	Weight only
Vital Signs and Pulse Oximetry	X	Includes body temperature, respiratory rate, seated/supine blood pressure, and heart rate. Blood pressure, respiratory rate, and heart rate should be measured after the participant has been seated quietly for at least 5 minutes.
Laboratory Tests ^c	X	Laboratory tests must be completed within 2 weeks of retreatment Cycle 1/Day 1 unless otherwise noted. For laboratory assessments, see Section 9.4.4 and Table 9.4.4-1
Urinalysis	X	See Section 9.4.4
Serology Tests	X	Repeat the following if > 6 months since last treatment: serum for hepatitis C antibody, hepatitis B surface antigen, HIV-1 and HIV-2 antibody (screening, and as mandated by local requirement), and hepatitis C RNA (reflex). For HCC participants: hepatitis B surface antigen, hepatitis B surface antibody, hepatitis B core antibody, hepatitis B deoxyribonucleic acid (DNA) polymerase chain reaction (PCR), hepatitis C antibody, and hepatitis C ribonucleic acid (RNA) PCR and hepatitis D antibody testing for those with concurrent hepatitis B infection.
Thyroid Function Tests	X	TSH with free T3 and free T4 (reflex only)
Serial Serum PK Sampling		PK/ADA sampling to be done at predose on Day 1 of all cycles; @ EOT and 30 and 60 day followup visits. PK sampling to be performed w/SAEs, with addition of ADA if suspected hypersensitivity reaction. No dose delay PK sampling to be done in Retreatment.

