All participants will be treated for up to 24 weeks (3 cycles) with monotherapy (Parts 1A and 2A) or combination therapy (Parts 1B and 2B), unless treatment discontinuation criteria are met earlier ([Section 8.1](#)). Participants with ongoing disease control (CR, PR or SD) or unconfirmed progressive disease, after completing approximately the initial 24 weeks of treatment, may be eligible for an **additional 3 cycles of study therapy** in both the monotherapy (Parts 1A and 2A) and combination therapy (Parts 1B and 2B). These participants will be selected on a case by case basis, after careful evaluation and discussion with the BMS Medical Monitor, to determine whether the risk/benefit ratio supports administration of further study therapy. Upon completion of 3 cycles of study therapy (or up to a maximum of 6 cycles if applicable), all participants will enter the safety follow-up period.

Individual participants with confirmed CR will be given the option to discontinue study treatment, on a case by case basis, after specific consultation and agreement between the Investigator and BMS Medical Monitor in settings where benefit/risk justify discontinuation of study therapy.

5.1.3 *Follow-up*

5.1.3.1 *Safety Follow-up Period*

For participants in Parts 1A, 1B, 2A and 2B, upon completion of 3 cycles of study therapy (or up to a maximum of 6 cycles if applicable), and once the decision is made to discontinue the participant from treatment, ie, at end of treatment (EOT), all participants will enter a safety follow-up period.

In Parts 1C and 2C, participants can receive study treatments up to a maximum of 2 years in the absence of disease progression or unacceptable toxicity. Once a decision is made to discontinue treatment, the participant will enter a safety follow-up period.

For participants who complete all scheduled cycles of therapy, the EOT visit will be the same visit as the last scheduled and completed on-treatment visit, and will be the start of the safety follow-

up period. For participants who do not complete all scheduled cycles of therapy, the EOT visit will be the most recent on treatment visit (with all available safety and response data), and will not need to be repeated. Accordingly, for these participants, this visit will be considered the start of the safety follow-up period.

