5.4.5 Rationale for Treatment Duration

Despite recent advances in immunotherapies for the treatment of cancer, the ideal treatment duration to achieve and perpetuate good durable response is still an area of ongoing investigation. Current clinical data on the time to response suggest that, most patients who show a response, do so within the first 24 weeks on therapy. At the time of this study's initiation, treatment with BMS-986207, alone or in combination with nivolumab, was limited to 24 weeks (3 cycles), with an option of an additional 24 weeks (3 cycles) based on evaluation of individual risk/benefit on a case by case basis.

Accumulating evidence from different clinical trials in which participants with different tumor types were treated with nivolumab or nivolumab combined with ipilimumab indicates that most responses generally occur early, with a median time to response of 2 to 4 months including responses observed in patients with NSCLC.^{36,37, 38} A recent analysis in a melanoma study suggests the majority of patients who discontinue nivolumab and/or ipilimumab for toxicity maintain disease control in the absence of further treatment.³⁹ For these reasons, treatments in Parts 1C and 2C will be given for up to 2 years in the absence of disease progression or unacceptable toxicity.

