7.4.1 Dose Limiting Toxicities

For the purpose of guiding dose escalation, DLTs will be defined based on the incidence, intensity, and duration of AEs for which no clear alternative cause is identified. The DLT period will be 28 days (4 weeks) in Parts 1A and 1B. The DLT period for Part 1C will be 42 days (6 weeks).

For the purpose of participant management, any AE that meets DLT criteria, regardless of the cycle in which it occurs, will lead to discontinuation of study drug unless the Investigator determines that only 1 of the agents must be discontinued due to toxicity attributed to that agent alone. Participants who withdraw from the study during the 4-week DLT evaluation period (6-week DLT evaluation period for Parts 1C and 2C) for reasons other than a DLT may be replaced with a new participant at the same dose level. The incidence of DLTs during the 4-week DLT evaluation period (6-week DLT evaluation period for Parts 1C and 2C) will be used in dose escalation decisions and to define the MTD. AEs occurring after the 4-week DLT period (6-week DLT evaluation period for Parts 1C and 2C) will be considered for the purposes of defining the RP2D upon agreement between the Sponsor, Medical Monitor, and Investigators.

Participants experiencing a DLT will not be retreated with study drug, and will enter the safety follow-up period of the study. DLTs occurring after the 4-week (or 6-week period for Parts 1C and 2C) DLT observation period will be accounted for in determining the RP2D for expansion.

AEs will be graded according to the NCI CTCAE v4.03.

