9.1 Efficacy Assessments

Efficacy assessments for the [REDACTED] activity of BMS-986207, alone, in combination with nivolumab, or in combination with nivolumab and ipilimumab will be based on tumor measurements, using RECIST v1.1, with CT and/or MRI, as appropriate. In Parts 1A, 1B, 2A, and 2B, assessments will be performed at baseline, q8w (\pm 1 week) during the treatment period, and q12w for the first year after discontinuation of study drug/EOT visit. Subsequently, they will continue to receive tumor assessment scans as per standard of care guidelines, or at a minimum of every 6 months up to 2 years following the last dose of study drug, or until disease progression/withdrawal of study consent. In Parts 1C and 2C, contrast-enhanced CT of the chest, CT/MRI of the abdomen, pelvis, and all other known and/or suspected sites of disease should occur every 6 weeks starting from date of first dose (\pm 7 days) for the first 12 months (week 48), then every 12 weeks (\pm 7 days) until the end of year 2, then every 12 weeks (\pm 14 days) thereafter until disease progression or treatment discontinuation, whichever occurs later. The same imaging modality must be used for all assessments, per RECIST v1.1 ([Appendix 5](#)). Tumor assessment should be performed prior to initiating next cycle of treatment. Unconfirmed PR/CR must be confirmed at least 4 weeks after initial assessment finding.

Only data for the procedures and assessments specified in this protocol should be submitted to the Sponsor or Designee on a CRF. Additional procedures and assessments may be performed as part of standard of care. However, data for these assessments should remain in the participant's medical record and should not be provided to the Sponsor or Designee, unless specifically requested from BMS or designee.

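### Imaging rules after stopping treatment conflict: three places require SD, PR or CR and others do not, leaving participants who stop before their first scan without a clear rule

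*Combined protocol and SAP*

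**What the plan says.** **Text with a response condition.** Section 5.1.3.2, headed for all six parts, says "Participants, with SD, PR, or CR, at the time of the EOT visit or at the time of study drug discontinuation, will continue" with 12-weekly assessments for the first year. The Synopsis response follow-up paragraph has the same condition. Table 2-5 footnote a reads "Only participants with SD, PR, or CR at EOT visit".

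**Text without it.** For Parts 1C and 2C, Section 9.1 schedules scans every 6 weeks from first dose to week 48, then every 12 weeks, "thereafter until disease progression or treatment discontinuation, whichever occurs later". Table 2-4 and the tumor-assessment note in Table 2-5 have the same end point ("until disease progression or treatment discontinuation, whichever occurs later"); the note covers all parts, with an 8-week interval outside 1C and 2C. For Parts 1A, 1B, 2A and 2B, Section 9.1 gives "q12w for the first year after discontinuation of study drug/EOT visit", again with no response category attached.

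**Stopping.** Section 7.4.1 says "any AE that meets DLT criteria, regardless of the cycle in which it occurs, will lead to discontinuation of study drug", except where toxicity is attributed to one agent alone; Section 7.4.4 lists further exceptions. For participants who do not complete all cycles, Section 5.1.3.1 says "the EOT visit will be the most recent on treatment visit (with all available safety and response data), and will not need to be repeated".

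**Response and endpoints.** Under Appendix 5 a timepoint without imaging is not evaluable (NE), and CR or PR needs confirmation at least 4 weeks later. ORR and the 24-week PFS rate are primary efficacy endpoints in Part 2C only (Table 4-1). The final analysis uses all treated participants, and PFS censoring is deferred to a statistical analysis plan (Section 10.3.1).

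**The concern.** A participant can meet DLT criteria and stop before the first post-baseline scan, due at week 6 in Parts 1C and 2C and week 8 elsewhere. The EOT visit is then one that has already taken place, so it prompts no scan, and the participant has none of the three categories that the restrictive text requires. Section 5.1.3.2 says what happens to those with SD, PR or CR and to those who have progressed. It is silent on those never scanned. A site could reasonably follow either set of rules.

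At stake are the Part 2C primary efficacy endpoints and the activity rule built on ORR. If two doses are studied in Part 2C and early toxicity stops differ between them, recordable ORR could also fall unequally. Section 5.4.5 cites a melanoma analysis suggesting that "the majority of patients who discontinue nivolumab and/or ipilimumab for toxicity maintain disease control in the absence of further treatment". That evidence is indirect for this setting, but it is a reason to observe outcomes in this group.

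**Working it through.** **Step 1. Apply each rule to one case.** Take a Part 2C participant who stops for toxicity before week 6, has had no scan and has not progressed.

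| Text | Serial imaging continues? |
|---|---|
| Section 5.1.3.2, Synopsis, Table 2-5 footnote a | Not provided for: NE is not SD, PR or CR |
| Section 9.1, Table 2-4, Table 2-5 note | Yes, until progression |

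Table 2-5 therefore contains both answers. The stated intervals also differ in Parts 1C and 2C: 12-weekly after stopping in Section 5.1.3.2, against 6-weekly to week 48 in Section 9.1.

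**Step 2. What remains under the restrictive text.** Table 2-5 appears to mark a tumor assessment at the Day 100 safety visit. Day 100 is 100/7 = 14.3 weeks after the last dose. With a last dose at week 0 or week 3, the scan falls at about week 14.3 or 17.3. Confirmation would be possible from 14.3 + 4 = 18.3 or 17.3 + 4 = 21.3 weeks, but no later scan is due. The result is one scan before week 24 and no confirmable response.

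**Step 3. Reproduce the plan's figures.** Section 10.1.3.2 uses n = 20 per dose, a Beta(1,1) prior and benchmarks of 36% and 56%. At 11/20, PP(ORR ≥ 0.56) = 0.451 and PP(ORR ≥ 0.36) = 0.961, so both activity criteria are met. At 10/20, PP(ORR ≥ 0.56) = 0.288, which fails the 40% criterion. The exact binomial P(X ≥ 11 | n = 20) is 0.065 at 36% and 0.626 at 56%, matching Table 10.1.3.2-1.

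**Step 4. Illustrate the ORR effect.** Let d be the share who stop unscanned and never have a confirmed response, and q the rate at which they would have responded. The documents give neither, so both are assumptions. With NE counted as non-response among all treated, the ORR bias is −d·q. If stoppers would have responded like the others, recordable ORR = true ORR × (1 − d):

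| d | Recordable ORR, true 56% | P(≥ 11/20) | Recordable ORR, true 36% | P(≥ 11/20) |
|---|---|---|---|---|
| 0 | 0.560 | 0.626 | 0.360 | 0.065 |
| 5% | 0.532 | 0.527 | 0.342 | 0.045 |
| 10% | 0.504 | 0.426 | 0.324 | 0.031 |
| 20% | 0.448 | 0.244 | 0.288 | 0.012 |

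If q = 0 the bias is zero at every d.

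**Step 5. Interim ORR on the response-evaluable set.** Someone never scanned, without clinical progression or death, is excluded (Table 10.2-1). With p the ORR in the others, the bias is p − [(1 − d)p + dq] = d(p − q). At p = 0.56 and d = 10% it is +5.6 points for q = 0, zero for q = 0.56 and −2.4 points for q = 0.80.

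**Step 6. 24-week PFS rate.** If the later plan censored these participants at day 1, Kaplan-Meier would return p, the rate in the others, and the bias would again be d(p − q). Assuming p = 50% and d = 10%, it is +2.0, 0 or −2.0 points for q = 30%, 50% or 70%. At d = 20% it is +4.0, 0 or −4.0 points.

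**The case against.** A reader might infer that these participants drop out of imaging altogether. The documents do not support that. In Part 2C, Section 9.1 and Table 2-4 keep them on 6-weekly scans, and the Table 2-5 note says the same. Section 5.1.3.2 expressly ends response evaluation only for those who have progressed. This objection stands: the defect is a conflict between rules, not an omission throughout.

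A reader might also take the 30% DLT target, or the 2 DLTs among 4 evaluable participants in Part 1C, as the early-stop rate. Neither is one. The 2 of 4 occurred at 1200 mg, where no more participants will be treated, and Part 2C uses doses judged tolerable in Part 1C. Not every DLT stops all treatment. Nor does every DLT precede the first scan: that scan has a window of week 6 ± 7 days (days 35 to 49) against a 42-day DLT period, and scans are not postponed when doses are delayed.

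The 11/20 rule is stated for 20 evaluable participants. Someone never scanned, without clinical progression or death, may not be among the 20, so the losses in Step 4 need that person to be counted, for example through a Day 100 scan. This limits the size but does not remove the problem, because an unconfirmed Day 100 response is exactly that case.

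Finally, counting NE as non-response can only lower the final ORR, which is conservative. That is true, but a conservative loss still reduces the chance of detecting real activity.

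**Conclusion.** The concern holds as a conflict between imaging rules for participants without a response category. It matters most in Part 2C, where ORR and the 24-week PFS rate are primary. Where the restrictive text is followed, a response in an early toxicity stopper could not be confirmed, and the all-treated ORR would be lowered by d·q.

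The fall from 0.626 to 0.527, 0.426 or 0.244 is an illustration. It rests on assumed stop shares of 5%, 10% and 20%, on equal response in stoppers, on their being counted among the 20, and on no confirmatory scan. The loss is zero if none would have responded.

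A stronger statement, that ORR and 24-week PFS are biased as planned, goes beyond the documents. Any effect depends on which rule sites follow. For PFS, censoring at or near baseline is not stated anywhere, the rule is still to be written, and Step 6 shows that the bias could go either way.

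**What to change.** In Section 5.1.3.2, the Synopsis response follow-up paragraph and Table 2-5 footnote a, replace the SD, PR or CR condition with: all participants without documented RECIST v1.1 progression at EOT, including those with no post-baseline assessment or a not-evaluable response.

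Reconcile these three passages with Section 9.1, Table 2-4 and the Table 2-5 note, so that Table 2-5 no longer contains two rules. Include the interval in Parts 1C and 2C, where 12-weekly and 6-weekly scanning after stopping are both written; changing eligibility alone would leave that conflict in place. When the censoring rules are drafted, state how participants with no post-baseline scan enter best overall response and PFS.

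The cost is wording in three places plus the reconciliation, and a few more follow-up scans. Most of those are already planned in Section 9.1, whose rules for scanning after discontinuation carry no response condition in any part.

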Efficacy Assessments: Efficacy assessments for the [REDACTED] activity of BMS-986207, alone, in combination with nivolumab, or in combination with nivolumab and ipilimumab will be based on tumor measurements, using RECIST v1.1, with computer tomography and/or magnetic resonance imaging, as appropriate, at baseline, every 8 weeks (\pm 1 week) for Parts 1A, 1B, 2A, and 2B or every 6 weeks for Part 1C and Part 2C during the treatment period, and every 12 weeks thereafter during the response follow-up period.

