Procedure	Safety Follow-up			Survival Follow-up	Response Follow-up ^a	Notes	
	Follow-up 1 30 Days ^b (± 7 days)	Follow-up 2 60 Days (± 7 days)	Follow-up 3 100 Days (± 7 days)	All Participants - Commence with Start of Safety Follow-up: Follow-up Every 12 Weeks until 2 Years After LAST Dose of Study Drug	Commences with Start of Safety Follow-up: Follow-up Done Every 12 Weeks for 1 Year After LAST Dose of Study Drug		
Pharmacokinetic (PK) Assessments							
Serial Serum PK and Immunogenicity Sampling	See Table 9.5-2 and Table 9.5-3 for pharmacokinetic and immunogenicity sampling schedule and Section 9.5 .						
Efficacy Assessments							
Tumor/Response Assessments			X		X	Contrast enhanced CT of the chest, CT/MRI of the abdomen, pelvis, and all other known and/or suspected sites of disease should occur every 8 weeks (6 weeks for Parts 1C and 2C) starting from date of first dose (± 7 days) for the first 12 months (week 48), then every 12 weeks (± 7	

Table 2-5: Follow-up Procedural Outline (All Participants)

Procedure	Safety Follow-up			Survival Follow-up	Response Follow-up ^a	Notes
	Follow-up 1 30 Days ^b (± 7 days)	Follow-up 2 60 Days (± 7 days)	Follow-up 3 100 Days (± 7 days)			
				All Participants - Commence with Start of Safety Follow-up: Follow-up Every 12 Weeks until 2 Years After LAST Dose of Study Drug	Commences with Start of Safety Follow-up: Follow-up Done Every 12 Weeks for 1 Year After LAST Dose of Study Drug	days) until the end of year 2, then every 12 weeks (± 14 days) thereafter until disease progression or treatment discontinuation, whichever occurs later. See Section 9.1 for further details.
Brain Imaging					X	As clinically indicated
Bone Scan					X	As clinically indicated
Subsequent Treatments (Anti-cancer)	X	X	X	X		
Assessment of Participant Survival Status				X		Participant status will be assessed by any documented clinic visit or telephone contact every 12 weeks.

Abbreviations: AE, adverse event; CR, complete response; CT, computed tomography; EOT, end of treatment; hCG, human chorionic gonadotropin; IU, international units; MRI, magnetic resonance imaging; PK, pharmacokinetic; PR, partial response;; SAE, serious adverse event; SARS-CoV 2, severe acute respiratory syndrome coronavirus-2; SD, stable disease; WOCBP, women of childbearing potential.

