9. STUDY ASSESSMENTS AND PROCEDURES

- Study procedures and timing are summarized in the Schedule of Activities. Protocol waivers or exemptions are not allowed. Adherence to the study design requirements, including those specified in the Schedule of Activities, is essential and required for study conduct.
- Study governance considerations in terms of compliance and reporting of AEs are available in [Appendices 2 and 3](#).
- All screening evaluations must be completed and reviewed to confirm that potential participants meet all eligibility criteria before enrollment. The Investigator will maintain a screening log to record details of all participants screened and to confirm eligibility or record reasons for screening failure, as applicable.
- Procedures conducted as part of the participant's routine clinical management (eg, blood count) and obtained before signing of informed consent may be utilized for screening or baseline purposes provided the procedure meets the protocol-defined criteria and has been performed within the timeframe defined in the Schedule of Activities.
- All immediate safety concerns must be discussed with BMS immediately upon occurrence or awareness to determine if the participant should continue or discontinue treatment

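### For Parts 1C/2C participants who stop treatment before week 48 without progression, the protocol sets two incompatible scan schedules, and one of them usually misses the week-24 landmark

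*Combined protocol and SAP*

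**What the plan says.** **Every 12 weeks, counted from the end of treatment.** Section 5.1.3.2, whose heading names Parts 1C and 2C, says that participants with SD, PR or CR at EOT or study drug discontinuation "will continue to have radiologic and clinical tumor assessments every 12 weeks for the first year after discontinuation of study drug/EOT visit". The Response Follow-up paragraph of the Synopsis says the same and exempts no Part. The Efficacy Assessments paragraph of the Synopsis names these Parts: "or every 6 weeks for Part 1C and Part 2C during the treatment period, and every 12 weeks thereafter during the response follow-up period". The response follow-up column of Table 2-5 (all participants) is headed "Commences with Start of Safety Follow-up: Follow-up Done Every 12 Weeks for 1 Year After LAST Dose of Study Drug". Its footnote a restricts that column: "Only participants with SD, PR, or CR at EOT visit".

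**Counted from first dose.** The note in the Tumor/Response Assessments row of the same table sets "6 weeks for Parts 1C and 2C) starting from date of first dose (± 7 days) for the first 12 months (week 48"), then 12-weekly. Section 9.1 gives the same schedule for Parts 1C and 2C, continuing "thereafter until disease progression or treatment discontinuation, whichever occurs later". Section 9.1 gives the step-down at discontinuation ("q12w for the first year after discontinuation of study drug/EOT visit") in its sentences on Parts 1A, 1B, 2A and 2B only.

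**Precedence.** None is stated. Section 9 says "Adherence to the study design requirements, including those specified in the Schedule of Activities, is essential and required for study conduct", but Table 2-5 belongs to that Schedule and carries both rules.

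**The concern.** For someone who stops without progression, the later of progression and discontinuation is progression. Section 9.1 therefore keeps the first-dose schedule running off treatment, while Section 5.1.3.2 replaces it with a sparser one on a different anchor. A site cannot follow both.

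The group is foreseeable. Under Section 7.4.1 an adverse event meeting DLT criteria generally ends study drug. Section 5.1.2.6 works with 33% as an acceptable DLT rate for the triplet. Section 5.4.5 cites a melanoma analysis in which most patients who stopped nivolumab and/or ipilimumab for toxicity kept disease control.

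Table 4-1 makes ORR, mDOR and PFSR at 24 weeks primary for Part 2C, with as few as 20 participants per dose level. All three depend on when scans are done, and a scan that was never done cannot be recovered at analysis.

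**Working it through.** **1. Scheduled scans after last dose, up to week 48.** Dosing visits are every 3 weeks (Table 2-4). Rule A (Section 9.1): weeks 6, 12, ..., 48 falling after last dose. Rule B (Section 5.1.3.2, anchored on last dose as in the Table 2-5 heading): last dose + 12, + 24, and so on. The Day-100 visit, which Table 2-5 also marks for a tumor assessment, falls at last dose + 100/7 = last dose + 14.3 weeks.

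| Last dose (week) | Rule A scans | Rule B scans (weeks) | Day-100 scan (week) | Rule B scan in weeks 23-25? |
|---|---|---|---|---|
| 0 | 8 | 4 (12, 24, 36, 48) | 14.3 | yes |
| 3 | 8 | 3 (15, 27, 39) | 17.3 | no |
| 6 | 7 | 3 (18, 30, 42) | 20.3 | no |
| 9 | 7 | 3 (21, 33, 45) | 23.3 | only by Day-100 |
| 12 | 6 | 3 (24, 36, 48) | 26.3 | yes |
| 15 | 6 | 2 (27, 39) | 29.3 | no |
| 18 | 5 | 2 (30, 42) | 32.3 | no |
| 21 | 5 | 2 (33, 45) | 35.3 | no |

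Rule A always has the week-24 scan. Rule B has it for 2 of 8 last-dose visits, or 3 of 8 with the Day-100 scan. The difference in scans is 3 to 5 per participant, or 2 to 4 if the Day-100 scan is counted.

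**2. Does the anchor matter?** Section 5.1.3.2 counts from discontinuation or EOT. For an anchor at week a, a + 12 or a + 24 falls in weeks 23-25 only if a is in weeks 11-13 or 0-1. Table 2-4 visits in weeks 0-21 are weekly to week 5, then at weeks 6, 9, 12, 15, 18 and 21. Only weeks 0, 1 and 12 qualify, so the landmark is still mostly missed.

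**3. Confirmation.** Appendix 5 requires a PR or CR to be confirmed at least 4 weeks after it is initially seen. With last dose at week 3, the first and confirming scans are at weeks 6 and 12 under Rule A and weeks 15 and 27 under Rule B. The Day-100 scan cannot confirm a response seen at week 15, because 17.3 - 15 = 2.3 weeks.

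**4. Participants with no post-baseline scan.** The first scheduled scan is at week 6. Someone who stops earlier has no scheduled scan from which SD, PR or CR could be assigned at EOT, so footnote a does not clearly admit them. Table 10.3.1-1 still counts them in the all-treated ORR denominator.

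**5. Size.** The plan's reference figure reproduces: P(X ≥ 11), X ~ Bin(20, 0.56), is 0.626, as in Table 10.1.3.2-1. A simulation then applied Rule B to early stoppers, with confirmed ORR set to 56% under Rule A. Its assumptions are not in the documents:
- response present from week 6 (60%) or week 12 (40%);
- exponential duration of response, median 9, 12 or 20 months;
- exponential PFS in non-responders, median 3 or 4 months;
- response unaffected by stopping, no new therapy, and progression dated at the next scan;
- 20%, 33% or 40% assigned to stop early (40% is 8 of 20, one below the Table 10.3.8-1 boundary of 9);
- last dose spread over weeks 0-21, or at week 0 or 3 only;
- participants who stop before week 6 still scanned 12-weekly.

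Results:
- P(at least 11 of 20) falls from 0.63 to 0.55-0.61 (spread) or 0.48-0.59 (early). If sites add a separate 4-week confirmation scan, it falls to 0.60-0.62 or 0.56-0.61.
- In responders: 0.48 corresponds to a true ORR of about 0.519, and (0.56 - 0.519) × 20 = 0.82. In the central case (33% stopping, median duration 12 months, Day-100 scan counted) ORR falls to about 53.5-54.6%, a loss of 0.3-0.5 responder in 20.
- PFSR at 24 weeks reads 0.5-3.1 points higher. Anchoring on an EOT visit 3 weeks after last dose, at 33% stopping, gives 2.4-3.5 points. The standard error at n = 20 is 10-11 points: √(0.7 × 0.3/20) = 0.102 and √(0.5 × 0.5/20) = 0.112.
- Observed median DOR moves by -4.0 to +7.5 weeks.

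**The case against.** **The texts may be reconcilable.** The Synopsis gives Parts 1C/2C a clear sequence: 6-weekly on treatment, 12-weekly in response follow-up. The first-dose wording also appears in the on-treatment Table 2-4, which cites Section 5.1.4, so its end-point clause may have been written for participants treated beyond progression. On that view this is carried-over wording. The explanation is plausible, but it does not remove the conflict: the same schedule, naming Parts 1C and 2C, stands in the follow-up table, and Section 9.1 gives the step-down only for the other Parts. It does mean that the defect is an internal inconsistency rather than a chosen design.

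**The stopping rates may be high.** Section 7.4.1 lets the investigator stop one agent only, and Section 7.4.4 lists further exceptions. The 33% is the mean of a Beta(1, 2) distribution, not a forecast of stopping. In Appendix 12 a dose is normally declared tolerable at an observed DLT rate of 0.236 or less. This stands, so the upper end of the simulated range should not be expected.

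**The effect is small.** This stands too. The PFSR shift is well inside the standard error, a 4-week confirmation scan removes much of the ORR loss, and Section 3.1 says no hypotheses are formally evaluated.

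**A stronger reading to avoid.** A reader might infer that Part 2C's dose comparison is biased, because the dose with more toxicity stops would be scanned less often. The direction is right if sites follow the 12-weekly rule and stopping differs by dose. But a second dose is at the sponsor's discretion (Section 5.1.2.7), and the documents give no stopping rates by dose.

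**Conclusion.** The contradiction is in the current text and needs correcting. For Parts 1C/2C participants who stop before week 48 without progression, the protocol gives two schedules with different intervals and anchors, and nothing ranks them. The scan counts, the missed week-24 landmark and the delayed confirmation follow from the schedules alone.

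The size is probably modest: about 1-3 points on PFSR at 24 weeks and less than one responder in 20. It rests on the assumed stopping rate and the other assumptions listed, including that participants who stop before week 6 are still scanned. If footnote a were applied strictly to them, their loss is not sized here.

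Two further inferences are not supported. Section 9.1 does not require 6-weekly scans until progression without limit; it steps down to 12-weekly after week 48. Nor does the 12-weekly rule make PFSR at 24 weeks inestimable: the Kaplan-Meier estimate can still be computed, but progression around the landmark is detected later. The reason to act is that binding text contradicts itself on the timing of primary-endpoint assessments and the correction is cheap.

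**What to change.** State one rule for Parts 1C and 2C:
- Participants who stop treatment without progression, including those with no post-baseline scan yet, stay on the Section 9.1 first-dose schedule until progression, subsequent anti-cancer therapy or withdrawal of consent.
- Limit the 12-weekly-from-EOT wording in Section 5.1.3.2, both Synopsis paragraphs, and the Table 2-5 response follow-up heading and footnote a to Parts 1A, 1B, 2A and 2B.
- Remove the 8-weekly first-dose schedule from the Table 2-5 note. For those four Parts it contradicts Section 9.1, which goes to 12-weekly after EOT, so narrowing the heading alone would leave the row inconsistent.

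If the sponsor prefers 12-weekly scans off treatment, keep the 6-weekly first-dose grid at least through week 24 and say so in both Section 9.1 and Table 2-5.

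Cost: no extra scans relative to Section 9.1. Relative to the 12-weekly rule, about 3-5 extra scans to week 48 for each participant whose last dose is in weeks 0-21 (2-4 if the Day-100 scan is counted). Sample size and analysis methods do not change.
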